# 7.3 Interim analysis

Both a Simon's optimal two-stage and Bayesian two-stage design were used to estimate sample size (see section 2.10 above) with the Simon's design yielding a slightly larger group for interim analysis (18 patients). Thus, we will plan to perform an interim analysis at 18 recruited patients who have received the ESPB and if 8 or more patients receive a second parenteral pain medication then the study will be ended for futility.

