# 2.10 Sample Size

- This study is a two-stage trial with one planned interim analysis for futility
- Based on the prior 30-month time period (as of May 2022), 572 out of 1071 patients (53.4%) presenting to the ED and meeting the inclusion criteria did not require a 2nd parenteral pain medication during the ED encounter. Thus, we estimate a baseline response rate of 55%.
- Prior work by Nobel et al.¹and Aydin et al.² suggests that no patient will require a second dose of any pain medication after ESPB, but we estimate a conservative response rate of 75% for treatment with ESPB.
- Using Simon's optimal two-stage design with these parameters and  $\alpha$  = 0.05,  $\beta$  = 0.10, we estimate that 18 subjects will be required at the interim analysis and 54 subjects will be required to complete this study.
- Using a Bayesian two-stage design, where interim analysis is planned at one-third total enrollment and a stopping rule if there is only a 10% probability of ESPB demonstrating a 75% response rate, we estimate that 45 total subjects (15 at interim analysis) will be required to achieve a 1.4% chance of stopping early and 95.2% chance of rejecting the null hypothesis.
- This study will aim to achieve a total enrollment of 60 subjects who receive ESPB to account for losses to follow up and withdrawals from the study. Up to 180 (3:1 ratio) historical controls will also be included in the study thus the total enrollment including both treatment and control patients is 240.

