#### 3.6 Outcomes

#### 3.6.1 Primary Outcome and rationale

The primary outcome will be the proportion of patients receiving a second parenteral pain medication in the ED after a single-shot ESPB is performed by a study investigator. We have reviewed historical data that suggests that the rate of response (percentage of patients that do not require a second parenteral pain medication) in patients with urolithiasis, and who receive a parenteral medication as the first analgesic in the ED (approximately 70% of all kidney stone patients), ranges from 47 to 57% for the years 2020 – 2022. The average response rate is 53.4% during this period which is in line with historical trends prior to the Covid-19 pandemic.

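### The stage 1 futility rule is applied only once 18 patients have had the block, although an 8th second-dose event fixes the stop sooner; a running count would spare about 2 blocks per trial under the null

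*Combined protocol and SAP*

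**What the plan says.** Section 2.10 sets out the design: "This study is a two-stage trial with one planned interim analysis for futility". It takes a null response rate of 55%, rounded up from the historical "572 out of 1071 patients (53.4%) presenting to the ED", and a target response rate "of 75% for treatment with ESPB". With alpha 0.05 and beta 0.10 it reports that under Simon's optimal design "we estimate that 18 subjects will be required at the interim analysis and 54 subjects will be required to complete this study".

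Section 7.3 turns this into an operating rule: "we will plan to perform an interim analysis at 18 recruited patients who have received the ESPB and if 8 or more patients receive" another parenteral analgesic dose, the study ends for futility.

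Section 3.6.1 fixes the outcome within the index visit: "The primary outcome will be the proportion of patients receiving a second parenteral pain medication in the ED" after the block. A response is the absence of such a dose.

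Sections 7.2 and 6.4 take the outcome from an EHR query, with manual chart review if needed. The data review in section 8.6.2, held at least monthly, names enrollment and adverse events. No section mentions a running count of second doses, a stop at the 8th, or a pause in enrollment before patient 18.

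**The concern.** A count of events can only rise. Once 8 of the patients treated so far have had a second parenteral dose, no result in the rest of stage 1 can bring the total below 8, and the futility decision is fixed. The plan evaluates the rule at 18 treated patients and has no means of recognising the boundary sooner. Any patient treated between the 8th event and patient 18 therefore adds nothing to the decision for which stage 1 was sized.

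What those patients receive is a needle procedure with up to 150 mg of ropivacaine (sections 5.2 and 5.3). Section 8.1 lists its risks, including local anesthetic toxicity, vascular puncture, pneumothorax and delay of other analgesia, and section 8.5 rates the ESPB arm slightly above minimal risk. A futility rule exists to limit exposure of this kind. Because the outcome is settled within one ED visit, acting sooner is practical here in a way that it is not in trials with long follow-up.

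**Working it through.** **Inputs.** Null response 0.55, target response 0.75, historical response 572/1071 = 0.534, alpha 0.05, beta 0.10, n1 = 18, n = 54 (section 2.10). Futility threshold: 8 or more events in 18 (section 7.3). An event is a second parenteral pain medication, so its probability is q = 1 − response rate.

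**Assumptions not in the documents.** Alpha is one-sided, as is usual for Simon's design; patients are independent; for the main figures, each outcome is known before the next block. Response rates of 0.60 and 0.65 are added only to show the range.

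**Step 1: reproduce the plan's design.** An exact binomial search for the smallest expected sample size under the null gives n1 = 18, stop at 10 or fewer responses, n = 54, and rejection of the null at 36 or more responses. Exact alpha is 0.0477 and power 0.9007. Ten or fewer responses in 18 is the same as 8 or more events, so 18, 54 and the threshold of 8 all match. (The final critical value comes from the search; the documents do not state one.)

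**Step 2: locate the 8th event.** Let K be the patient in whom it occurs. Then P(K = k) = C(k−1, 7) × q^8 × (1−q)^(k−8), for k = 8 to 18. For example, at q = 0.45, P(K = 18) = 19448 × 0.45^8 × 0.55^10 = 0.0828.

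- Probability of a futility stop = sum over k = 8 to 18. At q = 0.45 this is 0.6085, the same as the binomial probability of 8 or more events in 18.
- Probability that the 8th event comes before patient 18 = 0.6085 − 0.0828 = 0.5257, which is 86.4% of futility stops.
- Mean blocks avoided per trial = sum of P(K = k) × (18 − k) = 1.96.
- Mean blocks avoided per futility stop = 1.96 / 0.6085 = 3.2. The 8th event falls on average at patient 18 − 3.2 = 14.8 (median 15).
- The maximum saving is 18 − 8 = 10 blocks, with probability 0.0017 at q = 0.45.

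| True response | Futility stop | 8th event before patient 18 | Blocks avoided per trial | Per futility stop |
|---|---|---|---|---|
| 53.4% | 66.0% | 57.9% | 2.23 | 3.4 |
| 55% | 60.9% | 52.6% | 1.96 | 3.2 |
| 60% | 43.7% | 35.9% | 1.21 | 2.8 |
| 65% | 27.2% | 21.3% | 0.65 | 2.4 |
| 75% | 5.7% | 4.0% | 0.11 | 1.8 |

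**Step 3: expected sample size at 55%.** As written: 18 + 36 × (1 − 0.6085) = 32.1. With the boundary recognised at the 8th event: 32.1 − 1.96 = 30.1.

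**Step 4: delay in knowing the outcome.** If L further patients are treated before the 8th event is confirmed, the saving per trial is the sum of P(K = k) × max(0, 18 − k − L). At 55% this is 1.43 for L = 1, 0.99 for L = 2 and 0.65 for L = 3. The lag is an assumption; the documents give no ascertainment time.

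**Step 5: effect on error rates.** K is 18 or less exactly when there are 8 or more events in the first 18 patients. Every sequence of outcomes therefore leads to the same stop or continue decision, and a trial that continues has exactly the same data. The stop probability, alpha 0.0477 and power 0.9007 are unchanged.

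**Step 6: effect on the estimate in a stopped trial.** At 55%, the mean raw response rate given a stop is the sum of P(K = k) × (k − 8)/k, divided by 0.6085, which is 44.3%. With all 18 treated it is the sum over x = 0 to 10 of P(x responses in 18) × x/18, divided by 0.6085, which is 47.5%. Both lie below 55% because stopping selects poor runs; early recognition adds about 3 percentage points.

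**The case against.** The strongest reply is that nothing is wrong. One look at n1 is Simon's design as published and as named in section 2.10, and the stated figures reproduce exactly. Stopping within stage 1 is an optional refinement. This stands: a reader might infer a mis-specified futility rule, and the documents do not support that.

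A reader might also infer that patients will in fact be treated in a stage that has already failed, or that the plan commits the team to treating them. Neither follows. The extra blocks arise only if the 8th event falls before patient 18, which at the target response happens in 4.0% of trials. Section 7.3 is silent on what happens after an early 8th event; it does not order enrollment to go on.

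Quoting only the saving among stopped trials would overstate the gain, so the averages over all trials are given beside it. Larger savings would need a response rate below the 47 to 57% range in section 3.6.1, that is, a block that increases re-dosing. Nothing in the documents suggests one.

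Outcomes may not be known at once. The source is an EHR query, chart review may follow, and section 2.8 requires that the dose be for urolithiasis pain, which may need judgement. This stands and makes the main figures upper bounds.

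The remaining stage 1 patients do have value. Estimating complications is an objective in section 2.3, and 3 of 18 patients is a noticeable share. That is a legitimate reason for completing 18, but the plan does not give it.

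Finally, the trial is open label (section 2.5). A live count that treating clinicians can see might influence the decision to re-dose or how a dose is classified. This is a fair caution, and it is met by keeping the count within the study team.

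**Conclusion.** The point holds as a minor improvement in patient protection and efficiency. The futility rule is correctly derived, but it is tied to patient 18 with no provision for an earlier 8th event. If the block does no better than the 55% null, it is slightly more likely than not (52.6%) that the stop is fixed before patient 18. About 2 blocks per trial, or 3.2 per futility stop, would then be given without bearing on the decision. If the block works as assumed, the issue almost vanishes (4.0% of trials, 0.11 blocks). The figures rest on independent patients and on outcomes known before the next block; a lag of two patients halves the saving at 55% to about 1.0 block. Trial validity and error rates are not in question.

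**What to change.** Add to section 7.3 that the study team keeps a running count of second parenteral pain medications among ESPB patients, not shared with the treating clinicians. State that the existing boundary is met, and enrollment ends, when the 8th such event is confirmed among the first 18 ESPB patients. The threshold of 8 stays. If the team prefers to treat all 18 for safety or precision, it should say so in 7.3.

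The cost is a sentence or two and a tally, using the EHR and chart sources already planned. A stopped trial would have slightly fewer patients for safety and secondary outcomes, and its raw response rate would be biased slightly low; the report should say so.

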#### 7.4 Other outcomes

Other outcomes unique to study patients (received ESPB as part of this study) including change in pain score, follow up assessment outcomes, complications, and patient satisfaction will be analyzed before-after the ESPB, change over time, or descriptively as appropriate. Secondary outcomes derived from EHR query (ED operations metrics, opioid medication usage and prescriptions) will be analyzed for study patients in comparison to external controls. All comparisons to external control patients will be made using data collected via EHR query rather than prospectively collected data (investigator collected pain scores, patient satisfaction, follow survey results, etc.) which will be reported descriptively and without comparison to controls.

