# 2.2 Primary Objective

Determine the efficacy of the erector spinae plane block (ESPB) performed by emergency physicians (EPs) for the treatment of pain related to uncomplicated urolithiasis

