#### 3.6.2 Secondary Outcomes

- Difference in visual analog scale pain (1-10) from prior to procedure to first pain assessment after 60 minutes from completion of ESPB assessed by bedside nurse
  - Historic data from the U-M ED suggests that the median maximal pain reduction (last pain score minus first) in the ED is a mean reduction of 3.4 points (SD = 3.0) from a starting value of 7.9.
- ED operational quality metrics:
  - o Rate of admission to hospital
  - Rate of 72-hour return to the ED
  - ED length of stay
- Safety outcomes and complications at day 30

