#### 7 DATA ANALYSIS PLAN

# 7.1 Descriptive analysis and statistical testing

The primary exposure of interest is performance of ESPB for uncomplicated renal colic in the ED. We will describe the center and spread for all collected variables. Additionally, we will compare data from participants to historical control patients whose data is collected secondarily from query to the EHR. Continuous variables will be described by medians with interquartile ranges and differences will be assessed by two-sample t-test or Wilcoxon's rank sum test depending on distribution. Categorical variables will be described by counts with proportions and differences assessed using the Chi-squared test or Fisher's exact test where appropriate. An alpha = 0.05 will be considered the level of significance in all analyses.

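### Section 7.4 puts change in pain score under an uncontrolled before-after analysis while 4.4 promises a comparison with controls; a test against zero change would not measure the block's effect

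*Combined protocol and SAP*

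**What the plan says.** Section 2.2 sets the primary objective: "Determine the efficacy of the erector spinae plane block (ESPB) performed by emergency physicians (EPs) for the treatment of pain". The first-listed secondary outcome in 3.6.2 is the difference in pain score "from prior to procedure to first pain assessment after 60 minutes from completion of ESPB assessed by bedside nurse".

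Three sections bear on how that outcome is analysed.

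- Section 7.4 treats change in pain score as an outcome that only block recipients have: "change in pain score, follow up assessment outcomes, complications, and patient satisfaction will be analyzed before-after the ESPB, change over time", with descriptive reporting allowed as an alternative. The EHR-derived outcomes it then assigns to comparison with controls are ED operations measures and opioid use and prescribing; pain is not named. Its last sentence makes prospectively collected items, including investigator-collected pain scores, descriptive only.
- Section 4.4 says that, for a valid comparison between the groups, the pain scores recorded by the bedside nurse are the ones to be compared. Section 6.4 obtains nurse pain assessments by EHR query and uses the same query for controls.
- Section 7.1 states "An alpha = 0.05 will be considered the level of significance in all analyses". For continuous variables it says "differences will be assessed by two-sample t-test or Wilcoxon's rank sum test depending on distribution". It names no paired test.

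Section 3.6.2 also gives a historical figure for this ED. It is described as the "median maximal pain reduction (last pain score minus first) in the ED" and reported as follows: it "is a mean reduction of 3.4 points (SD = 3.0) from a starting value of 7.9".

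**The concern.** A before-after test in one group has zero mean change as its null. That is not the question in 2.2. Every participant has already had one parenteral analgesic dose (4.2), renal colic pain varies over time, and patients are enrolled while in pain. Scores can therefore fall after the procedure with no contribution from the block, and the historical figure shows that they do fall over an ED visit in patients treated before this trial. Rejecting zero change cannot separate the block from the first dose, later analgesia, the natural course or regression to the mean.

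What is at stake is the trial's conclusion on pain. Taken literally, 7.4 gives the nurse-assessed secondary outcome only the uncontrolled analysis, and leaves the choice between a before-after analysis and description open until the data are in. A significant fall could then be read as efficacy. Under 4.4 the same outcome would be compared with controls. The plan does not say which section governs.

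**Working it through.** **The plan's own figure.** The documents give no sample size or power for the pain outcome. The only frequentist size calculation is for the primary outcome: Simon's optimal design with response rates 0.55 and 0.75, alpha 0.05 and beta 0.10 (2.10). An exact binomial search gives 18 patients at stage one (stop at 10 or fewer responders) and 54 in total (reject the null above 35), with attained alpha 0.0477 and power 0.9007. This matches the stated 18 and 54, so the group sizes are not in question.

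**Inputs for the pain test.**
- n = 60 block recipients (target in 2.10), with 54 and 45 as the Simon and Bayesian totals.
- SD of change 3.0 (3.6.2). This is a first-to-last figure; the SD over the post-block window is not given.
- Alpha 0.05 (7.1), taken as two-sided because sidedness is not stated.
- Block effect set to zero. The background fall d in the post-block window is not given, so a range is used: 0.5, 1.0, 1.3, 1.7 (half of 3.4) and 3.4 points.

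**Smallest significant mean fall.** This is t(0.975, n−1) × SD/√n. At n = 60 the standard error is 3.0/√60 = 0.387, and the threshold is 0.775 points. At n = 54 it is 0.819, and at n = 45 it is 0.901.

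**Chance of p < 0.05 with an inert block.** This is the power of the paired t-test from the noncentral t distribution, with noncentrality λ = d/(SD/√n). For d = 1.0 and n = 60, λ = 1.0/0.387 = 2.58.

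| Background fall d | λ at n = 60 | n = 45 | n = 54 | n = 60 |
|---|---|---|---|---|
| 0.5 | 1.29 | 0.19 | 0.23 | 0.25 |
| 1.0 | 2.58 | 0.59 | 0.67 | 0.72 |
| 1.3 | 3.36 | 0.81 | 0.88 | 0.91 |
| 1.7 | 4.39 | 0.96 | 0.98 | 0.99 |
| 3.4 | 8.78 | >0.999 | >0.999 | >0.999 |

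At n = 60 a background fall of 0.26 points already doubles the nominal 5%. If the SD lies between 2 and 4 instead of 3.0, the n = 60 figure at d = 1.7 runs from above 0.999 down to 0.90.

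**The controlled comparison.** In 20,000 simulated trials of 60 block patients and 180 controls, all with change drawn from a normal distribution with mean 3.4 and SD 3.0, the two-sample t-test was significant in 5.1%. The before-after test was significant in all of them. The detectable difference between groups is (z for alpha/2 + z for power) × 3.0 × √(1/60 + 1/180). At 80% power this is (1.960 + 0.842) × 3.0 × 0.149 = 1.25 points; at 90% it is 1.45. Both results treat the controls as exchangeable and their change as measured over a comparable window.

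**The case against.** The strongest reply is that the plan commits to no such test. Section 7.4 offers description as an alternative, 7.1 names only two-sample tests, and setting an alpha level does not turn every analysis into a test. The change in pain score in 7.4 may mean the investigator's one-hour score (5.4), which the end of 7.4 makes descriptive, while 4.4 already provides the controlled comparison of nurse scores. Much of this stands: the paired test is inferred, and a controlled analysis is planned. It does not settle the matter, because 7.4 does not say which score it means, omits pain from its comparison list, and so conflicts with 4.4 over an outcome defined by nurse assessment. Nor is a time point defined for controls, who have no procedure.

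A reader might infer that the before-after test is near certain to be significant for an inert block. The documents do not support that. The 3.4 points run from first to last ED score and so can include the effect of the first dose; the trial's window opens after that dose. Near certainty needs a background fall of about 1.7 points or more. A reader might also carry the point over to the follow-up items. That does not hold either: duration of pain control, complications and satisfaction with the procedure have no pre-block value.

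It can also be said that a 95% CI for the within-patient change is the same test against zero in another form. That is correct, which is why the interval needs an explicit statement that it is not evidence of efficacy.

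**Conclusion.** The point holds as a conflict between 7.4 and 4.4, with a conditional statistical consequence. If 7.4 governs and the change is tested against zero, the false-positive rate for a block effect is about 25% at a background fall of 0.5 points, 72% at 1.0 and 99% at 1.7 (n = 60), instead of 5%. This rests on the inferred two-sided paired test, on an SD of 3.0 carrying over to the post-block window, and on a background fall that the documents do not supply. The direction does not depend on the exact value: any appreciable background fall inflates the rate. The matter is confined to a secondary outcome. The primary analysis is compared with matched controls (7.2), the futility rule uses only second parenteral medication (7.3), and no decision in the plan depends on pain change.

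**What to change.** Amend 7.4 to agree with 4.4:

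- Make the comparison of EHR nurse-recorded pain change between ESPB patients and matched controls the only inferential pain analysis.
- Define the measure in the same way in both groups: for example first-to-last ED score, or change from a stated time anchor that is also assigned to controls.
- Report the within-patient before-after change as a mean with 95% CI, with no p-value, and state that it is not evidence of the block's efficacy.

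The cost is a few sentences; the nurse scores are already in the EHR query (6.4). There is a small downside. First-to-last change includes time before the block and any rescue analgesia, so it may dilute a real effect. A time anchor for controls lessens the first problem but has to be specified in advance.

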#### 8 RISK ASSESSMENT

# 8.1 Potential Risk to Subjects

This study is a single treatment arm trial of ESPB for uncomplicated renal colic to investigate efficacy and complications. Prior studies did not report any major or minor complications as a result of ESPB performed by emergency physicians. However, in prior studies performed perioperatively by anesthesiologists, the following complications were identified: local anesthetic toxicity or allergy, infection or bleeding of the soft tissue overlying the needle insertion site, vascular puncture, pneumothorax, and failed block. Based on prior literature, complications are considered extremely rare because the potential space superficial to the T8 transverse process (site of injection to create plane block) is far from the spinal cord, pleura and major blood vessels. Additional risks to participants include risk of delay in care or other analgesia medication as well as temporary discomfort (lasting less than 1 hour) due to the procedure. Additional risks to both participants and external controls (whose data is secondarily collected from EHR query) are loss of confidentiality.

